1 PROTOCOL SUMMARY

1.1 SYNOPSIS

Title:	Pilot Study of an Optic-to-Audio Device in a Pediatric Cohort with CLN3-related conditions or Low Vision
Study Description:	This is a pilot study of an augmentative visual device, OrCam MyEye 2 (OrCam), in pediatric individuals with CLN3-related conditions or low vision. We hypothesize that, given the relatively simple design and operating procedure of the device, the use of the OrCam by study participants will be safe and feasible. We also hypothesize that the device will enhance their ability to obtain visually based information.
Objectives:	
Primary Assess the safety and feasibility of OrCam use by children with CLN3 or low vision.
 
Secondary Assess the effectiveness of OrCam use by children with CLN3 or low vision.
 
Exploratory Assess the feasibility and effectiveness of OrCam use in CLN3 versus non-CLN3 groups. Optimize methods for assessing efficacy of visual accommodation/assistive devices for the CLN3/NCL population

Endpoints:	
Primary 1) Adverse events during the use of OrCam. 2) Feasibility test. 3) Feasibility questionnaire. 4) Device use diary. The assessment periods will be 1 week at study site and 1 month at home.
 
Secondary 1) Function test of using OrCam. 2) Ability questionnaire.
 
Exploratory 1) Function test. 2) Feasibility, Ability, Applicability questionnaires.

Study Population:	30 individuals age 6-18 years with low vision (20 with CLN3-related conditions, 10 without CLN3) of any gender, demographic, geographic location who meet study eligibility criteria.
Phase:	Not applicable
Description of Sites/Facilities	The NIH Clinical Center will be the only site enrolling participants.
Enrolling Participants:	
Description of Study Intervention:	The study uses the OrCam MyEye 2, a 22.5-g portable, eyeglass-mounted device that converts camera-captured inputs to auditory outputs. Its advertised functions include text reading, facial recognition, and product identification. The study participants and

Abbreviated Title: Pediatric Optic-to-Audio Device Study

[figure not shown]
Version Date: October 25, 2022

parents/guardians will be trained on how to use the device. Evaluations for primary and secondary endpoints will be done following 1 week and 1 month of device use.

Study Duration: 24-36 months.

Participant Duration: 1-2 months

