1.3 SCHEDULE OF ACTIVITIES (SOA)

Procedures	Screening ^{a,d} Up to Day -1	Enrollment Baseline Day 1	Day 2 ^b	Day 3 to 4 ^b	1-Week Evaluations Day 5 ^b	Day 6-11 ^b	Day 12 ^b	Day 13-18 ^b	Day 19 ^b	Day 20-25 ^b	Day 26 ^b	Day 27-32 ^b	1-Month Evaluations Day 33 ^{b,c}
Informed consent ^c	X												
Demographics ^c	X												
Medical history ^c	X												
Physical exam ^d	X												
Vital signs ^d	X												
Ophthalmic evaluation ^d	X												
Neuropsychologic evaluation ^c	X												X ^{d or h}
Audiologic evaluation ^d	X												
UBDRS ^{c,e}	X												
Device training ^{c,f}		X ^d	X ^d	X ^{d or h}	X ^d	X ^h	X ^h	X ^h	X ^h				
Device use ^g			X ^{d or h}	X ^{d or h}		X ^h	X ^h	X ^h	X ^h	X ^h	X ^h		
Adverse events review ^c					X ^{d or h}		X ^h		X ^h		X ^h		X ^{d or h}
Feasibility test ^{c,i}		X ^d			X ^d								X ^{d or h}
Feasibility questionnaire ^{c,j}					X ^{d or h}								X ^{d or h}
Function test ^k		X ^{l, d}			X ^{l, d}								X ^{m, d or h}
Ability questionnaire ⁿ		X ^d			X ^{d or h}								X ^{d or h}
Applicability questionnaire ^o		X ^d											
Quality of Life questionnaires ^p		X ^d											X ^{d or h}
Phlebotomy ^d	X												
Research biospecimen collection ^q	X												

^a Screening evaluations can be done under 18-CH-0002 protocol if participant consented to co-enroll, or under this protocol. Previous evaluations/procedures within stated time frames (**Section 8.1.2**) will be accepted in lieu of repeating.

Abbreviated Title: Pediatric Optic-to-Audio Device Study

Version Date: March 8, 2022

^b +/- 2 days, except for Day 2 to 4 range may be +2 days

^c By in-person or remote technology methods

^d At NIH CC

^e Only in participants with CLN3-related conditions who are not co-enrolled in study 18-CH-0002.

^f **Appendix J** - OrCam MyEye 2 User Guide, Software Version 8.2-EN, Jan 2020.

^g By participant for minimum of 15-30 minutes per day. If participant/parents/guardians encounter issues with device use, they may contact the study team and a video- or audioconference will be scheduled as appropriate.

^h At home

ⁱ **Appendix A.** To be administered by study team to participant

^j **Appendix B.** To be administered by study team to participant if able, and parents/guardians

^k **Appendix C.** To be administered by study team to participants.

^l Full Function Test done with evaluator and participant at NIH CC or partial Function Test done via remote technology (e.g., videoconferencing).

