3 OBJECTIVES AND ENDPOINTS

OBJECTIVES	ENDPOINTS	JUSTIFICATION FOR ENDPOINTS
Primary		
To assess: a) safety and b) feasibility of using OrCam MyEye 2 by children with CLN3 or low vision.	
a) Adverse events b) Feasibility test, Feasibility questionnaire, and Device use diary (see Section 9.4.2)
 
The assessment periods will be 1 week at study site and 1 month at home.
	
a) Collection of adverse event data is a standard method for evaluating safety in clinical trials. b) No validated, standardized tool is available to evaluate the feasibility of augmentative communication devices such as the OrCam. We modified the feasibility questionnaire used in an adult study [26] to provide appropriate adaptation for the pediatric cohort.

Secondary		
To assess the efficacy of using the OrCam by	1) Function Test – Efficacy Scores (see Section 9.4.3)	No validated, standardized tool is available to evaluate the efficacy of augmentative communication

OBJECTIVES	ENDPOINTS	JUSTIFICATION FOR ENDPOINTS
children with CLN3 or low vision.	2) Ability questionnaire (see Section 9.4.3) The assessment periods will be 1 week at study site and 1 month at home.	devices such as the OrCam. We developed a Function Test based on the device's advertised functions, our observations of the pediatric cohort in the Natural History study, and the one used in an adult study [26], to provide age and ability appropriate assessments.
Exploratory		

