6 STUDY INTERVENTION

6.1 STUDY INTERVENTIONS(S) ADMINISTRATION

6.1.1 Study Intervention Description

OrCam MyEye 2 is an FDA class 1 device (<https://www.accessdata.fda.gov/scripts/cdrh/cfdocs/cfRL/rl.cfm?lid=397540&lpcd=HPG>). The main components include a 13 megapixels camera, a 3.7V DC (nominal 320mAH) battery, and ancillary charging and glass-mounting supplies. The OrCam MyEye 2 is available in only one size that has dimensions of 76x21x14.9 mm, and weighs 22.5 g. Additional visual and descriptions of the device, its set-up and functions are provided in **Appendices I-K**. The use of the OrCam in this study will be according to the manufacturer's specifications. The device is not intended as an implant and does not present potential for serious risk to the health, safety, or welfare of a subject. Due to its risk profile, the device should be considered a non-significant risk device.

Participants will be trained and asked to use the device for at least 30 minutes daily as indicated in the **Schedules of Activities**. All participants meeting eligibility criteria will enroll in the 1-week study and be exposed to the device use for 5 days. Participants may enter the additional 1-month study if parents/guardians/participants endorse desire to continue using the device at home.

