7.2 PARTICIPANT DISCONTINUATION/WITHDRAWAL FROM THE STUDY

Prior to removal from study, effort will be made to have all participants complete a safety evaluation approximately 1 week following the last use of study device.

Participants are free to withdraw from participation in the study at any time upon request.

An investigator may discontinue or withdraw a participant from the study for the following reasons:

- Significant study intervention non-compliance
- If the participant meets an exclusion criterion (either newly developed or not previously recognized) that precludes further study participation
- Participant has completed the study follow-up period
- Death
- Screen Failure

The reason for participant discontinuation or withdrawal from the study will be recorded on the Discontinuation/Withdrawal Case Report Form (CRF). Participants who sign the informed consent form but do not receive the study intervention, i.e. the activities on enrollment/baseline

Abbreviated Title: Pediatric Optic-to-Audio Device Study

Version Date: March 8, 2022

day, may be replaced. Participants who sign the informed consent form, receive the study intervention, and subsequently withdraw, or are withdrawn or discontinued from the study, will not be replaced.

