8.3 SAFETY AND OTHER ASSESSMENTS

The specific timing of procedures/evaluations to be done at each study visit are captured in **Section 1.3, Schedule of Activities**. Direct evaluations (e.g., Device training, Feasibility test) at Screening, Enrollment Baseline Day 1 and 1-Week Evaluations Day 5 visits will be done onsite at the NIH CC. Non-direct evaluations (e.g., surveys and questionnaires) and evaluations on other study days can be done onsite or at home.

- 1. Medical History and Physical Exam.** A medical history and physical exam will be obtained. For CLN3 participants, medical history will ascertain information that is being collected as part of a national CLN3 registry (<https://rarediseases.info.nih.gov/diseases/5897/neuronal-ceroid-lipofuscinosis-3>). Participation in the registry is not a requirement and caretakers or participants will be given the option of having medical information submitted to the registry. The history forms contain common data elements recommended for rare diseases research. Parents and participants may also be asked what elements of the disease are clinically relevant to them, in order to obtain insight into pertinent outcome measures in designing future therapeutic trials. Information from outside records or NIH visits, and from reports by participants and family members will be collected and reviewed.
- 2. Anthropomorphic Measures and Clinical Photography.** Anthropomorphic measures including weight, length/height, and head circumference will be obtained at each visit.
- 3. Feasibility Questionnaire.** Participants/parents/guardians will be asked to complete a questionnaire relating to their experience using the OrCam device (**Appendix B**). The questionnaire can be completed on paper or web-based format at the time points indicated in the **Schedule of Activities**.

4. **Device Training.** A study team member will provide verbal instructions to participant and parents/guardians on the assembly, set-up, and use of the OrCam. The instructions will be based on the User Guide (**Appendix J**). At the end of the training session, understanding of how to use the device will be documented by the trainer.
5. **Device Use Diary.** As described in **Section 6.4 Study Intervention Compliance**.

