9.4.2 Analysis of the Primary Endpoints

Adverse events and Device use diary data will be provided using descriptive statistics.

Feasibility Test

Data analysis. Participants' scores will be the sum of items 1 to 5 and will range from 0 to 5. Analysis will consist of summary descriptive statistics (mean, standard deviation, median, proportion of participants at each score level). No formal statistical tests will be conducted. Interpretation of results will be rule-based.

Rules for data interpretation. Device use is feasible if at baseline, 1-week, or 1-month 50% or more of total number of participants score 3 or greater out of 5.

Feasibility Questionnaire

Data analysis. Participants' scores will be the sum of items 1 to 11 and will range from 0 to 11. Analysis will consist of summary descriptive statistics (mean, standard deviation, median, proportion of participants at each score level). No formal statistical tests will be conducted. Interpretation of results will be rule-based.

Rules for data interpretation. Device use is feasible if at 1-week or 1-month 50% or more of total number of participants score 6 or greater out of 11.

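### The Feasibility Test rule lets the Day 1 score alone declare device use feasible, even if the 50% threshold is missed after both 1 week and 1 month of use

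*Combined protocol and SAP*

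**What the plan says.** Section 9.4.2 scores the Feasibility Test from 0 to 5, summarises it descriptively without a hypothesis test, and reads it by a rule: "Device use is feasible if at baseline, 1-week, or 1-month 50% or more of total number of participants score 3 or greater" (out of 5).

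The synopsis (Section 1.1) gives the timing of these endpoints differently: "Evaluations for primary and secondary endpoints will be done following 1 week and 1 month of device use". The synopsis and Section 3 both describe the assessment periods as one on-site week and one month at home.

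Other places bear on what a Day 1 score means:

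- The Schedule of Activities (Section 1.3) marks the Feasibility Test on Days 1, 5 and 33. Device training is also marked on Day 1. The first mark in the device-use row is Day 2.
- Section 8.3 places "Direct evaluations (e.g., Device training, Feasibility test) at Screening, Enrollment Baseline Day 1 and 1-Week Evaluations Day 5 visits" on site.
- Section 7.2 treats Day 1 activities as receipt of the intervention: it allows replacement of those who consent but "do not receive the study intervention, i.e. the activities on enrollment/baseline" day.
- Section 6.1.1 says: "All participants meeting eligibility criteria will enroll in the 1-week study and be exposed to the device use for 5 days". That fits Days 1 to 5.
- Section 9.3.2 speaks of feasibility evaluations on both sides of device use.

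The Feasibility Questionnaire rule in Section 9.4.2 names only 1 week and 1 month. That questionnaire is first given on Day 5, so its rule raises no conflict.

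**The concern.** The three visits in the Feasibility Test rule are alternatives, so any one of them is sufficient. A Day 1 result at the threshold gives the verdict whatever happens later, and nothing else in the plan limits this.

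The Feasibility Test is a component of the primary endpoint, and its interpretation rests entirely on this rule. The stated verdict could therefore be 'feasible' when the threshold was missed after 1 week and again after 1 month of use. The planned proportions at each score level would show the later failure, but the prespecified conclusion would contradict them. Section 9.2 makes pilot information on feasibility a main aim of the trial.

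**Working it through.** **Inputs from the plan.** N = 30 (Sections 4.1 and 9.1); pass mark 3 or more out of 5; threshold 50% of all participants; visits at Day 1, 1 week and 1 month. The plan gives no expected pass rate, alpha or power for this rule, so there is no figure to reproduce. The simulations in Section 9.4.3 concern the Function Test.

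**The logic.** The threshold is 0.50 × 30 = 15 children.

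| Passing at Day 1, 1 week, 1 month | Rule as written | Rule on 1 week or 1 month only |
|---|---|---|
| 15, 14, 14 | feasible | not feasible |
| 15, 0, 0 | feasible | not feasible |

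This result needs no assumption about pass rates.

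**Chance of passing at one visit.** With X the number passing, X ~ Binomial(30, p), P(X ≥ 15) is:

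| Assumed p | 0.20 | 0.30 | 0.40 | 0.50 | 0.60 |
|---|---|---|---|---|---|
| P(X ≥ 15) | 0.02% | 1.7% | 17.5% | 57.2% | 90.3% |

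**Chance of passing at one or more visits, visits independent.** For k visits with the same p, this is 1 − (1 − a)^k, where a is the single-visit probability. At p = 0.40, a = 0.1754:

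- two visits: 1 − 0.8246² = 0.320
- three visits: 1 − 0.8246³ = 0.439

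**Visits correlated within a child.** The same child is tested each time, so independence overstates the gain. I used a latent-normal model with exchangeable within-child correlation of 0.3 or 0.8 and 200,000 simulations. The pass rate at each post-use visit is assumed to be 40%, below the threshold, and all 30 are scored. Entries are percentages at correlation 0.3 / 0.8.

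| Assumed Day 1 rate | 1 week or 1 month only | Day 1 added | Verdict resting on Day 1 alone |
|---|---|---|---|
| 20% | 30.7 / 26.8 | 30.7 / 26.8 | 0.0 / 0.0 |
| 30% | 30.7 / 26.8 | 31.5 / 26.9 | 0.8 / 0.2 |
| 40% | 30.7 / 26.8 | 40.7 / 32.9 | 10.0 / 6.1 |
| 50% | 30.7 / 26.8 | 67.2 / 60.4 | 36.5 / 33.7 |

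**Incomplete continuation.** The 1-month study is voluntary (Sections 6.1.1 and 6.3). Suppose 20 of 30 continue and the other 10 stay in the denominator as not passing. The post-use chance is then 17.8 / 17.4%. With Day 1 added it is 17.8 / 17.4, 18.9 / 17.9, 30.7 / 26.7 and 62.6 / 58.9% at Day 1 rates of 20, 30, 40 and 50%. At a 40% Day 1 rate the gain is 30.7 − 17.8 = 12.9 or 26.7 − 17.4 = 9.3 points.

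**The case against.** The best case for the rule as written has four parts.

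1. **The synopsis is a summary.** Its sentence covers secondary endpoints too, and those also need Day 1 data. Day 1 falls within the on-site week, and Section 3 refers the reader to Section 9.4.2 for detail. This stands in part: the synopsis does not forbid a Day 1 test. But the secondary rules use baseline only as the comparator. In the Feasibility Test rule, baseline is a sufficient condition for success.

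2. **The rule looks deliberate.** Each rule in Section 9.4.2 names exactly the visits at which its instrument is scheduled, and the study hypothesis stresses that the device is simple to operate. Early operability may well interest the sponsor. That supports reporting it, not letting it override failure after use.

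3. **Day 1 is not free of exposure.** This stands. Training occurs that day, Sections 7.2 and 6.1.1 are consistent with counting it, and the extracted device-use row is not a reliable marker of first contact. The items of Appendix A are not in the available text, so whether the test comes before or after training on Day 1 cannot be determined. In either order, Day 1 precedes the week of use named in the synopsis.

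4. **The effect may be nil and the consequences limited.** Section 2.3.1 expects early discomfort and frustration to ease as the child gets used to the device, which points to lower Day 1 scores and little or no gain from counting them. This is an uncontrolled pilot; the test is one of three feasibility components, with no rule for combining them; and visit-level proportions will be reported. All of this stands. However, a later shortfall need not mean lost skill. Continuation is voluntary, children who withdraw after receiving the intervention are not replaced (Section 7.2), and the denominator is all participants. If children give up the device, Day 1 could be the only visit that meets the threshold.

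It is also true that the 'or' between 1 week and 1 month by itself lifts the chance at p = 0.40 from 17.5% to 27–31%. That is a separate matter.

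**Conclusion.** The concern holds. As written, the Feasibility Test can return 'feasible' on Day 1 results alone after failure at both post-use visits, which does not fit the timing in the synopsis. The conclusion follows from the wording and does not depend on assumed rates.

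The numerical size does depend on them. With post-use rates of 40% and all 30 scored, counting Day 1 adds nothing at a Day 1 rate of 20%, under 1 point at 30%, and 6 to 10 points at 40%. The chance of 'feasible' reaches 60–67% only if Day 1 performance (50%) exceeds later performance, which nothing in the documents predicts.

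The finding is limited to the Feasibility Test. It should be fixed because it is a stated decision rule for a primary-endpoint component.

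**What to change.** Strike baseline from the list of visits in the Feasibility Test rule, so that it is met only if at least half of all participants score 3 or more out of 5 at 1 week or at 1 month. Add one sentence saying that Day 1 scores are reported descriptively as initial operability. If the sponsor wants a Day 1 criterion, state it as a separate result that cannot by itself give the feasible verdict.

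The cost is one word deleted and one sentence added; no new data are needed. The verdict becomes slightly harder to reach:

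- True rate 60% at every visit, all 30 scored: from 99.6 / 97.9% to 98.4 / 96.3% (correlation 0.3 / 0.8).
- Same rate, 20 of 30 continuing and the rest counted as not passing: from 98.5 / 96.2% to 91.1 / 90.4%.
- Day 1 rate 20%, later rates 60%, all 30 scored: no loss (98.4 / 96.3% either way).

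Optional and separate: report the 1-week and 1-month results separately, and say whether children who do not enter the voluntary 1-month study count in the denominator.

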9.4.3 Analysis of the Secondary Endpoint(s)

Function Test – Efficacy Scores

Data analysis. Participants' scores will be the sum of items 1 to 7 combining levels a & b and will range from 0 to 14, and the mean duration to complete each task. Analysis will consist of change in scores and mean duration to complete each task from baseline to 1 week and 1 month). No formal statistical tests will be conducted. Interpretation of results will be rule-based.

Rules for data interpretation. Device use is efficacious if at 1-week or 1-month compared to baseline:

- 25% or more of total number of participants increased score by at least 30%
- 25% or more of total number of participants decreased time by at least 30%

Below are some simulations of the power of a paired-sample test for change from baseline, using a sample size of 10 participants. This provides a sense of the possible characteristics of the data and for justifying the sample size.

Simulations for tasks-completed scores

Each simulation study used 1000 replications with $N = 10$. For each replication, baseline and post-baseline sets of scores were randomly generated. Means, standard deviations, and paired-samples t-tests of difference scores (Post-baseline – Baseline)

were computed. Power was computed by the percent of replications (out of 1000) with t-test p-values less than or equal to 0.05. Baselines were generated by randomly selecting, with replication, scores from 0 to 5 with equal probability, 1/6. The baseline range matched the baseline values reported in the adult study. Post-baseline scores included a specified number of baseline cases randomly selected without replacement to improve by 30% (Baseline \times 1.30). Cases with baseline values = 0 were excluded from random selection since percentage change from 0 is undefined.

Simulation 1. Based on the decision rule of 25% of total participants, 3 cases (rounded up since 25% of N= 10 is 2.5) were randomly selected to improve 30% from baseline and the other 7 cases did not improve. *Results: power = proportion of 1000 p-values <= 0.05 = 0.37.*

Simulation 2. 3 cases randomly selected to improve 30% and 7 cases improved by 1 point. *Results: power = proportion of 1000 p-values <= 0.05 = 1.0.*

Simulation 3. 4 cases randomly selected to improve 30% and 6 cases did not improve. *Results: power = proportion of 1000 p-values <= 0.05 = 0.95.*

Simulation 4. 4 cases randomly selected to improve 30%, 6 cases improved by 1. *Results: power = proportion of 1000 p-values <= 0.05 = 1.0.*

Simulation 5. 2 cases randomly selected to improve 30% and 8 cases did not improve. *Results: power = proportion of 1000 p-values <= 0.05 = 0.00.*

Simulation 6. 2 cases randomly selected to improve 30%, 8 cases improved by 1. *Results: power = proportion of 1000 p-values <= 0.05 = 1.0.*

Simulations with baseline values 1 to 5, # cases improving 30%: 2 to 5; # cases improving by 1: 0 to 3; # cases no improvement: 4 to 8. (For any simulation run, # cases improving 30% + #cases improving by 1 + # cases not improving = 10).

Results: These simulations correct for the problem that percentage improvement is undefined when baseline = 0. When stipulating that percentage improvement is 30% for as few as 2 or 3 cases, power is greater than .99 when only 1 to 3 other randomly selected cases improve by 1 from baseline. Power will be higher if participants' scores improve more than 1 over baseline.

Based on these simulations, a test of efficacy using a paired-samples t-test with N = 10 would be adequately powered provided that post-baseline scores are likely to improve from baseline. Whether or not a sample of 10 is large enough to make conclusions about different characteristics of the sample group is not addressed.

Ability Questionnaire

Data analysis. Proportions of participants with scores 3 or greater in all items from 1-12. No formal statistical tests will be conducted. Interpretation of results will be rule-based.

Rules for data interpretation. Device use is efficacious if there is a 25% increase in the proportion of participants scoring 3 or greater in all items at 1-week or 1-month as compared to baseline.

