4 STUDY DESIGN

4.1 OVERALL DESIGN

Individuals with CLN3 are anticipated to have vision loss and intellectual disability, but with preserved auditory function. We **hypothesize that an auditory-based assistive technology with a simple operating procedure, such as the OrCam, will be safe and feasible for use in a pediatric population, including those with CLN3, and will enhance their ability to obtain visually based information.** We propose a pilot study of 20 study participants to evaluate the safety, feasibility, and efficacy of using the OrCam in a cohort of the CLN3 pediatric population. Since no information is available on the safety, feasibility and efficacy of the OrCam in the

Abbreviated Title: Pediatric Optic-to-Audio Device Study

Version Date: March 8, 2022

pediatric population, we also propose enrolling 10 pediatric participants with low vision from non-CLN3-related causes. The primary and secondary objectives will be assessed using data from all 30 participants.

In this 2-cohort (CLN3 and non-CLN3), open-label, single-center study, we aim to determine:

- 1) the safety and feasibility
- 2) the potential clinical efficacy

of the use of OrCam in children, including individuals with CLN3.

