4.2 SCIENTIFIC RATIONALE FOR STUDY DESIGN

Currently, there is no device similar to the OrCam available or in accepted use for individuals with CLN3. In addition, there is also no data available on the use of this device in children with low vision. Thus, a combined cohort of pediatric participants with and without CLN3-related disorders will optimize recruitment potential, and provide preliminary information for evaluation of feasibility and efficacy in pediatrics, and specifically in individuals with CLN3-related conditions. To assess efficacy, we will use the study participants' baseline data as controls. This option encompasses the least number of confounding factors for a cohort of small size.

In the CLN3 natural history study (18-CH-0002), accrual rate averages at 8-10 per year. Not all of these individuals will meet the eligibility criteria for this proposed study. However, we anticipate, based on experience with interventional trials of other rare diseases, that families hesitant to participate in an observational study would be more open to participating in an interventional study. Given these considerations, we anticipate an accrual rate of 5 participants per year and a reasonable potential to enroll 20 CLN3 participants over 2-3 years. We have also discussed potential eligible participants with local Ophthalmology groups (Howard University, Johns Hopkins, NEI), and the anticipated number for pediatric individuals with low vision and not CLN3-related condition is estimated to be in the same range. We plan to screen up to 50 participants.

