9.4 STATISTICAL ANALYSES

9.4.1 General Approach

For comparisons of before and after device intervention in the same participant and correlation calculations, statistical significance will be determined by corresponding parametric (e.g., paired t-test and Pearson correlation) or non-parametric (Wilcoxon Rank sum test and Spearman correlation) methods. A p value < 0.05 will be considered significant and between 0.05 and 0.10 will be considered a trend. Multiple comparisons will be corrected by appropriate post-hoc analysis.

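### The Function Test score rule counts children who rise by 30% and ignores those who fall as far, so retest variation alone can meet it, at a rate set by a retest SD the plan does not give

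*Combined protocol and SAP*

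**What the plan says.** The Function Test efficacy score in section 9.4.3 is the "sum of items 1 to 7 combining levels a & b and will range from 0 to 14". The decision rule opens "Device use is efficacious if at 1-week or 1-month compared to baseline" and lists two criteria: "25% or more of total number of participants increased score by at least 30" per cent, and "25% or more of total number of participants decreased time by at least 30" per cent. No word joins the two. The same section says: "No formal statistical tests will be conducted. Interpretation of results will be rule-based".

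Section 4.1 sets the denominator: "The primary and secondary objectives will be assessed using data from all 30 participants". Section 4.2 sets the comparator: "To assess efficacy, we will use the study participants' baseline data as controls".

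Section 9.4.1, by contrast, names parametric and non-parametric tests for within-child before/after comparisons and adds "A p value < 0.05 will be considered significant".

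Section 9.4.3 also reports simulated power for a paired t-test with 10 participants. Baselines are drawn evenly from 0 to 5. Selected cases improve by 30% or by 1 point, and no child's score falls.

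**The concern.** The rule looks in one direction only. A child whose score rises by 30% counts for the device, and a child whose score drops by 30% counts for nothing. On a short whole-point scale, some children will move by that much from one sitting to the next whatever the device does. With no concurrent control, no test and a choice of two visits, nothing in the rule separates such movement from benefit.

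The section's simulations do not fill the gap. They evaluate a paired t-test rather than the 25%/30% rule, and they contain no scenario in which nothing changes. Section 3 says that no validated tool exists for this purpose, and the documents give no retest reliability and no expected responder rate without benefit.

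What is at stake is how far the word efficacious can be trusted. Section 9.2 says the pilot data will feed the power calculation of a later efficacy trial, so a verdict produced by noise could mislead that step.

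**Working it through.** **1. The plan's own figures.** I re-ran its six simulations (paired t-test, N = 10, baselines uniform on 0-5). A one-sided 0.05 test gives 0.377 for Simulation 1 (stated 0.37), 0.966 for Simulation 3 (stated 0.95), 0.00 for Simulation 5 and 1.0 for the other three, so the stated values are reproduced. A two-sided test gives 0.00 and 0.31 for Simulations 1 and 3. The reason is simple: with 3 positive and 7 zero differences, t cannot exceed √(3×9/7) = 1.96, and the two-sided critical value on 9 df is 2.26. The sidedness is not stated. None of these figures is a false-positive rate for the 25%/30% rule.

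**2. What the rule needs.** 25% of 30 is 7.5, so 8 risers. On whole points, a rise of at least 30% is 1 point from a baseline of 1-3 and 2 points from a baseline of 4-6.

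**3. Exact binomial.** Let p be each child's chance of a spurious rise of at least 30%. The chance of passing at one visit is P(X ≥ 8) with X ~ Bin(30, p):

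| p | 10% | 15% | 20% | 25% | 30% |
|---|---|---|---|---|---|
| P(pass) | 0.8% | 7.0% | 23.9% | 48.6% | 71.9% |

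This passes 5% once p exceeds 14.0%, or 12.3% if two visits are treated as independent chances.

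**4. Simulation with no true change (assumed noise).** Each child has a fixed true score. Baseline, 1-week and 1-month scores add independent normal error, rounded and held within 0-14. Zero baselines never count as risers. The table shows how often the score criterion is met at either visit:

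| True scores | SD 0.5 | SD 1 | SD 1.5 | SD 2 |
|---|---|---|---|---|
| 0-5 | 5% | 39% | 53% | 54% |
| 4-10 | 0% | 4% | 40% | 71% |
| 0-14 | 0% | 3% | 17% | 33% |

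For true scores 0-5 and SD 1, on average 6.1 children rise and 7.4 fall by at least 30%. More children worsen than improve, yet 39% of trials pass (25% at a single visit). If a rise from zero were counted, 39% would become 83%.

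Other noise models give, at either visit: binomial scores, 80% for true levels 1-5 and 88% for levels 3-7; noise of one point up or down, each with probability 20%-25%, about 24%-37% for levels 1-5.

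**5. The time criterion.** With no true change, the time criterion alone is met at either visit in 2%, 36% and 72% of trials at an assumed within-child CV of 0.2, 0.3 and 0.4. For true scores 0-5, SD 1 and CV 0.3, with score and time errors independent, requiring both criteria at the same visit gives 11%, and accepting either gives 62%.

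**6. Adding the paired comparison.** If the lower limit of the two-sided 95% CI for mean change must also exceed 0, the false-positive rate at one visit is about 3% or less in these models. This is expected, because the favourable tail of that test is 2.5%.

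**The case against.** Three points on the other side have force.

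First, the size rests on noise that the documents do not describe. At SD 0.5, or at SD 1 with true scores of 4-10, the score criterion passes about 5% of the time or less. The 0-5 baseline range was chosen to match the adult study, and children scored on 0-14 may start elsewhere. The binomial model treats all items as equally hard, and items of differing difficulty would be less noisy. A reader might infer from the upper figures that the trial would most likely declare efficacy with a useless device. The documents do not support that: they give no retest SD, and the figures cover only one of two listed criteria.

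Second, this is a secondary endpoint of a pilot, and section 9.4.3 does analyse change in scores, so falls would be visible. That lowers the stakes. It does not bring the falls into the verdict.

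Third, a reader might conclude that the count should become risers minus fallers, with the 25% threshold kept. That would control false positives fairly well, but it misses more real benefit than necessary. With binomial noise, true levels 1-5 and half the children truly gaining 2 points, a net-25% rule passes at one visit 45% of the time, against about 59% for the existing rule plus a paired comparison.

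**Conclusion.** The defect stands. The score criterion is one-directional, has no benchmark for what chance would produce, and can be met at either of two visits by retest variation alone. On the plan's own baseline range, the rate at either visit is about 5% at a within-child SD of 0.5 point, 39% at 1 point and 53% at 1.5 points. Across the other baselines and noise models tried, it runs from about 1% or less to 88%.

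These results assume 30 children with data at all three visits, independent errors, no true change and zero baselines not counted as risers. They show what the rule can do and do not measure this trial's error rate. Requiring both criteria would lower the rate and accepting either would raise it, and the text leaves that open. Practice effects were not modelled and would add to spurious rises.

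**What to change.** In section 9.4.3:

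- Keep the 25%/30% responder criterion, but call the device efficacious only if the paired before/after comparison already named in section 9.4.1 also favours it, meaning the 95% CI for mean change in score lies above 0.
- Judge this at 1 week, with 1 month as supportive. Section 8.2.1 plans the whole test face to face at baseline and 1 week, but allows a remote subset at 1 month, and section 6.3 makes the 1-month phase voluntary.
- Delete the statement for this endpoint that no formal tests will be run. This also removes the conflict with section 9.4.1.
- State whether the score and time criteria are both required.
- Tabulate children falling by at least 30% beside those rising.

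The cost is a few sentences and one table column, with no new data or visits. The drawback is that the rule becomes harder to meet and can miss a modest benefit: about a 59% chance of passing at one visit if half the children truly gain 2 points under binomial noise. The paired comparison guards against symmetric noise only. It cannot separate device benefit from practice, and the report should say so.
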